3.3 OUTCOME MEASURES

3.3.1 Efficacy Outcome Measures

Efficacy assessments will include the ESSDAI, ESSPRI, and the SF-36. ESSDAI and ESSPRI will also be measured at screening in order to assess eligibility for the study.

The primary efficacy outcome for this study is:

- Proportion of patients showing a clinically relevant decrease in ESSDAI score from baseline after 12 weeks.

where a clinically relevant decrease in ESSDAI score is defined as a decrease of ≥ 3 points.

Secondary efficacy outcomes for this study are as follows:

- Proportion of individuals showing a clinically relevant decrease in ESSPRI score after 12 weeks where a clinically relevant decrease in ESSPRI score is defined as a decrease of ≥ 1 point.
- Change from baseline in ESSDAI, ESSPRI and SF-36 scores after 12 weeks.
- Change from baseline in each of the individual components of the ESSPRI (dryness, fatigue and pain) after 12 weeks.

where a clinically relevant decrease in ESSPRI score is defined as a decrease of ≥ 1 point.

3.3.2 Pharmacodynamic Outcome Measures

The pharmacodynamic outcome measures for this study are as follows:

- Change from baseline in tear flow rate.
- Change from baseline in salivary flow rate.
- Change from baseline in auto-antibody titres.
- Change from baseline in erythrocyte sedimentation test (ESR).
- Change from baseline in cathepsin S mass and activity in plasma, tears and saliva.
- Change from baseline in circulating numbers of defined sub-populations of white blood cells.
- Change from baseline in biomarker concentrations.

3.3.3 Pharmacokinetic Outcome Measures

RO5459072 plasma concentration data will be pooled with data from other studies ([Study WP29542](#) and [Study BP29772](#)) for population pharmacokinetic modelling. The modelling results will be reported separately.

3.3.4 Safety Outcome Measures

The safety outcome measures for this study are as follows:

- The incidence and severity of AEs.
- The incidence of SAEs or withdrawals because of AEs.

- The incidence of out-of-reference-range values for vital signs and ECGs, and laboratory tests.
- Change from baseline in vital signs and ECGs, and laboratory tests by visit.

3.3.5 Exploratory Outcome Measures

The exploratory outcomes for this study are as follows:

- Comparisons of the performance of alternative composite endpoints (e.g., Sjögren's response index [SSRI-30]) as predictive markers of drug treatment response.
- Change from Week 12 to follow-up for ESSDAI, ESSPRI and SF-36 scores in each treatment group.
- Comparisons of drug treatment effects between genotypes.
- Patterns of use of selected concomitant medications.

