Based on the observation that cathepsin S enzyme expression is increased after treatment with a cathepsin S inhibitor, there is a theoretical possibility acute rebound phenomena (i.e., re-emergence of symptoms at a severity worse than at baseline) may occur following discontinuation of RO5459072 treatment. However, because cathepsin S enzyme expression should return to normal soon after discontinuation of RO5459072, any pharmacodynamic rebound should be transient and is considered unlikely to manifest as changes in disease activity or symptoms.

Patients who choose to participate in the optional sub-study will have labial salivary gland biopsies performed at the beginning and end of the study. Labial biopsies are minimally invasive, routinely used for clinical diagnostic purposes ([Vitali et al 2002](#)) and have potential utility as an outcome measure in clinical studies ([Fisher et al 2015](#)). Nevertheless, there is a risk of sequelae from the biopsy procedure: the incidence of permanent neurological damage is estimated to be ~0.17% ([Varela Centelles et al 2014](#)). Therefore, biopsies will only be performed on consenting individuals at selected study centers with experience of performing biopsies, i.e., centers where biopsies are routinely performed as part of normal clinical practice by experienced practitioners.

In summary, non-clinical data provide the necessary rationale that RO5459072 may provide a treatment benefit for patients with Sjögren's syndrome. No significant safety concerns have been identified about the use of RO5459072 in patients with Sjögren's syndrome. Where theoretical risks from RO5459072 treatment have been identified from non-clinical studies, appropriate clinical safety monitoring measures are implemented. Hence, the risks to participants in this study are considered acceptable.

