2.3 EXPLORATORY OBJECTIVES

The exploratory objectives for this study are as follows:

To investigate the effects of RO5459072 treatment on:

- cathepsin S enzyme mass and activity.
- sub-populations of circulating white blood cells.
- biomarkers connected to Sjögren's syndrome.
- biomarkers of extracellular matrix degradation.

Additionally:

- To explore the influence of covariates on the effects of RO5459072 treatment.
- To explore alternative composite endpoints as measures for evaluating effects of drug treatment.
- To explore the effects of RO5459072 treatment on the use of concomitant medications.
- To explore the occurrence of acute rebound phenomena on disease activity and symptoms following discontinuation of study drug treatment.

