Efficacy and pharmacodynamic assessments will be made at baseline and intervals during the treatment period, thereby allowing changes from baseline in each individual and the speed of onset of any treatment effect to be evaluated. In addition, efficacy assessments will also be made at the follow-up visit in order to explore the occurrence of acute rebound phenomena following discontinuation of study drug treatment. Rebound phenomena (i.e., re-emergence of symptoms at a severity worse than at baseline) are a theoretical possibility based on the observation that cathepsin S enzyme expression is increased after treatment with a cathepsin S inhibitor ([Payne et al 2014](#)).

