6.6.2 Secondary Efficacy Endpoints

Secondary endpoints that are binary will be analyzed using similar methods used for analyzing the primary endpoint.

Continuous secondary endpoints will be analyzed using a Mixed Model for Repeated Measures (MMRM) approach incorporating all observed data up to 12 weeks of treatment. The MMRM will include the absolute change from baseline as the dependent variable. The fixed effects in the model will include treatment, visit (week), treatment-by-visit (weeks) interaction, along with baseline score as continuous covariates. An unstructured variance-covariance structure will be applied to model the within-patient errors, and the restricted maximum likelihood method will be used for estimating the variance components. The denominator degrees of freedom will be estimated using *the Kenward-Roger approximation*.

The least squares mean of change from baseline for each treatment group together with a 95% CI will be calculated from the MMRM model for each visit. At Week 12, the placebo-corrected difference will be estimated from the same MMRM model and will be used to test the null hypothesis of zero difference.

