6.9 EXPLORATORY ANALYSES

Exploratory analyses will be conducted as deemed appropriate.

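### Rebound is defined against baseline, but its only listed outcome is the change from Week 12, so faded benefit and true rebound give the same result

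*Combined protocol and SAP*

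**What the plan says.** **Definition.** Section 3.2.5 states: "Rebound phenomena (i.e., re-emergence of symptoms at a severity worse than at baseline) are a theoretical possibility". Section 1.4.2 uses the same definition when it raises the risk: "acute rebound phenomena (i.e., re-emergence of symptoms at a severity worse than at baseline) may occur following discontinuation of RO5459072 treatment". Both sections take baseline as the reference.

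**Objective and purpose of the visit.** Section 2.3 lists as an exploratory objective: "To explore the occurrence of acute rebound phenomena on disease activity and symptoms following discontinuation of study drug treatment". Section 3.2.5 gives this as the reason for collecting efficacy data after treatment: "efficacy assessments will also be made at the follow-up visit in order to explore the occurrence of acute rebound phenomena".

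**Outcome.** Section 3.3.5 and the synopsis list one outcome that uses those data: "Change from Week 12 to follow-up for ESSDAI, ESSPRI and SF-36 scores in each treatment group". Its reference is Week 12, and it is described per arm.

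**Other places where a baseline-referenced measure could appear.** The secondary efficacy outcome in Section 3.3.1 stops at Week 12: "Change from baseline in ESSDAI, ESSPRI and SF-36 scores after 12 weeks". The repeated-measures model in Section 6.6.2 is an "approach incorporating all observed data up to 12 weeks of treatment", so it excludes the follow-up visit. Section 6.9 says only: "Exploratory analyses will be conducted as deemed appropriate".

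**Data collected.** Appendix 1 schedules ESSDAI and ESSPRI at baseline, Week 12, follow-up and early termination. It schedules SF-36 at baseline, Week 6 and Week 12 only.

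**The concern.** The definition asks whether a patient is worse after stopping than before starting. The listed outcome asks whether a patient is worse after stopping than at the end of treatment. The answers differ whenever the score moved during treatment, which is what an effective drug should bring about. A patient with ESSDAI 10 at baseline, 4 at Week 12 and 10 at follow-up scores +6 on the listed outcome, yet has only returned to the starting point.

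At stake is the one planned check on a risk that the benefit-risk section raises and judges unlikely to show clinically. As written, a worsening after Week 12 cannot be attributed either to rebound or to ordinary loss of effect. The larger the benefit that fades, the larger the apparent rebound.

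**Working it through.** **Inputs.** From Section 6.1: a 3-point ESSDAI difference, SD 5.0 for change from baseline, 35 patients per arm, two-sided alpha 0.05. From Appendix 1: follow-up 14 days (±7) after the Week 12 visit. Not in the documents, so assumed: the SD of the Week 12 to follow-up change (5, range 3 to 6); in the simulations, an SD of change from baseline of 5 at each visit (range 4 to 6) and a correlation between the Week 12 and follow-up changes of 0.5 (range 0.3 to 0.7).

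**The plan's own figure.** A two-sample t-test with difference 3, SD 5.0 and 35 per arm has power 69.7% (70.9% by the normal approximation). This reproduces the stated figure of about 70%, so the inputs are being read as the plan intends.

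**Identity.** For any patient with all three visits:

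(follow-up − Week 12) = (follow-up − baseline) − (Week 12 − baseline)

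Mean changes in ESSDAI, where positive is worse:

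| Case | Week 12 − baseline | Follow-up − baseline | Listed outcome |
|---|---|---|---|
| A. 3-point benefit fully lost, no rebound | −3 | 0 | 0 − (−3) = +3 |
| B. No benefit, then a true 3-point rebound | 0 | +3 | +3 − 0 = +3 |

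The listed outcome is identical in A and B. The change from baseline separates them.

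**How case A would look in one arm of 35.** The 95% CI half-width is t(0.975, 34 df) × SD/√35. At SD 5 this is about 2.03 × 5/5.92 = 1.7, so the arm would show +3.0 (1.3 to 4.7). At SD 3 the interval is 2.0 to 4.0, and at SD 6 it is 0.9 to 5.1. All exclude zero, although on average the patients are only back at baseline.

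In simulation, the listed outcome's interval lay wholly above zero in about 93% of trials in both A and B (68% to nearly 100% over the assumed range). The baseline-referenced interval did so in about 2.5% of trials in A and 93% in B (82% to 99%).

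**Partial loss.** Case A assumes that all the benefit is gone by follow-up. If 1.5 points are lost, the SD 5 interval is 1.5 ± 1.7, or −0.2 to 3.2. If 1 point is lost, it is 1.0 ± 1.7, or −0.7 to 2.7. The distortion is proportional to the benefit lost.

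**Rebound in a minority.** Suppose every patient has a 3-point benefit at Week 12, 10% then worsen by 9 points (to 6 above baseline) and 90% keep the benefit. The mean listed outcome is 0.10 × 9 = +0.9, with an interval above zero in about 14% of simulated trials (10% to 21%). The mean change from baseline is −3 + 0.9 = −2.1, which hides it too. Only a patient-level count shows this pattern.

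**The case against.** **Week 12 is a legitimate reference.** The objective concerns what follows discontinuation, and the Week 12 change isolates that period. A baseline reference alone would count a patient who worsened on treatment and barely moved afterwards. This stands: both references are needed, and the Week 12 change should stay.

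**The information is largely present.** Change from baseline to Week 12 is estimated by arm. For patients with both visits, adding the mean Week 12 to follow-up change recovers the mean change from baseline to follow-up. Placebo is reported as well, so an informal contrast is possible. This also stands, and it rules out saying that the objective cannot be answered. What the text lacks is a specified baseline-referenced measure with its CI, a placebo contrast and a patient-level count.

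**A separate analysis plan may supply it.** Section 6 defers analysis details to one, and none beyond the protocol's own Section 6 is in the supplied text. Such a plan could add the measure, but the outcome would still be listed with the Week 12 reference.

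**Stronger readings that a reader might infer.**

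- *An ineffective drug that causes rebound would go unnoticed.* It would not. With no benefit, Week 12 is about baseline, and case B shows the rebound in full on either measure.
- *The plan has a 70% chance of declaring a false rebound.* The 69.7% comes from a between-arm test that the plan does not specify for this outcome. It borrows the SD for change from baseline and assumes the full 3 points are lost in about two weeks. The same test at SD 5 gives 24% if 1.5 points are lost and 13% if 1 point is lost. Section 3.2.4 expects clinical effects to take weeks or months to appear; nothing in the documents says how quickly they fade.
- *This would create a false safety signal.* The outcome is exploratory and is not among the safety outcomes in Section 3.3.4.

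**Conclusion.** The point holds as a mismatch between a definition and its outcome. Followed as written, the listed outcome cannot distinguish faded benefit from rebound: with a 3-point benefit fully lost, or a 3-point rebound from no benefit, it reads +3 either way. This follows from the identity and needs no distributional assumption.

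How large the effect would be in this trial is not known, because it depends on the benefit achieved and the share lost by follow-up. The CIs and simulated frequencies above are illustrations under assumed SDs and correlations.

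That rebound could be missed altogether is the weaker part. It applies mainly when a minority rebounds and the arm mean conceals it, or when a patient stops early and has no Week 12 value.

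The SF-36 part of the outcome cannot be computed from the schedule in Appendix 1. Section 3.1.1 nevertheless lists quality of life among the assessments made at follow-up, so the two need reconciling.

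The change is worth making, but its reach is limited to one exploratory objective.

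**What to change.** In Section 3.3.5 and the synopsis:

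1. Keep the Week 12 to follow-up change, labelled as the measure of what happens after stopping.
2. Add the change from baseline to follow-up in ESSDAI and ESSPRI.
3. Add the proportion of patients worse at follow-up than at both baseline and Week 12. For example, require worsening from baseline of at least 3 points on ESSDAI or 1 point on ESSPRI, the sizes that the protocol already uses for relevant improvement. Requiring worsening from Week 12 as well keeps patients who only worsened on treatment from being counted as rebound.
4. Report items 2 and 3 by arm and as RO5459072 minus placebo with 95% CI, labelled exploratory.
5. State how patients without a Week 12 value are handled, including those who stop early.
6. Reconcile SF-36: either remove it from this outcome or align the schedule with it.

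Items 1 to 5 cost some wording and one extra exploratory table, because ESSDAI and ESSPRI are already scheduled at baseline, Week 12 and follow-up in both arms. Item 6 needs new data only if SF-36 is added at follow-up. The primary and secondary analyses do not change.

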3.3.6 Optional Sub-study Outcome Measures

Patients consenting to also participate in the optional sub-study will undergo MSG biopsies at baseline and Week 12. Biopsy samples will be processed for histological examination.

The outcomes for the optional sub-study are as follows:

- Change from baseline in focus score (number of lymphocytes per 4 mm²).
- Change from baseline in numbers of defined sub-populations of infiltrating lymphocytes.
- Subjective evaluation of changes from baseline in minor salivary gland (MSG) structure.

Other exploratory analyses may include, but not be limited to, changes in leukocyte and stromal subpopulation numbers and degree of activation.

4. MATERIALS AND METHODS

4.1 CENTERS

This is a multi-center, multi-country study to be conducted in the US and Europe. Additional sites may be included for back-up purposes and may be activated if needed.

Administrative and Contact Information, and List of Investigators are provided separately.

4.2 STUDY POPULATION

Patients with primary Sjögren's Syndrome will be enrolled into this study. Adults between 18 and 75 years old, diagnosed according to AECG criteria, with moderate to severe disease activity and symptoms based on ESSDAI and ESSPRI score can be enrolled in the study. The study will require approximately 70 patients.

Approximately 30 patients will be enrolled in the optional sub-study.

4.2.1 Recruitment Procedures

Patients will be identified for potential recruitment per site-specific recruitment plans.

4.2.2 Inclusion Criteria

Patients must meet all of the following criteria for study entry:

1. Males and females 18 to 75 years of age, inclusive.
2. Patient willing to give written informed consent and to comply with the study procedures and restrictions.
3. Primary Sjögren's syndrome diagnosed previously according to the revised American-European Consensus Group (AECG) criteria.
4. European League against Rheumatism (EULAR) Sjögren's Syndrome Disease Activity Index (ESSDAI) score ≥ 5 .
5. EULAR Sjögren's Syndrome Patient Reported Index (ESSPRI) score ≥ 5 .
6. Elevated serum titers at screening of anti-Sjögren's-syndrome-related antigen A (anti-SSA) and/or anti-SSB antibodies at screening.
7. Negative pregnancy test at screening and baseline (women only), and agreement to comply with measures to prevent pregnancy and restrictions on sperm donation (see Section 4.5.5).

4.2.3 Exclusion Criteria

1. A diagnosis of secondary Sjögren's syndrome according to the revised AECG criteria.
2. Severe complications of Sjögren's syndrome, such as vasculitis with renal, neurologic or cardiac involvement; interstitial lung disease and severe myositis,
3. Systemic immunosuppressant therapy (e.g., abatacept, azathioprine, ciclosporin, etanercept, tofacitinib), cyclophosphamide or B cell depleting therapy (e.g., rituximab anti-CD20 therapy) within 6 months prior to the screening visit. Low dose methotrexate treatment (i.e., oral doses ≤ 20 mg weekly) is, however, permitted.
4. Corticosteroid therapy exceeding 7.5 mg prednisone equivalents per day.
5. Mechanically stimulated whole salivary flow rate at baseline of < 0.1 mL/min.
6. A positive test result for hepatitis B (HBV), hepatitis C (HCV), or human immunodeficiency virus (HIV), *or* tuberculosis, or any other active viral, fungal, yeast or bacterial infection at the screening visit.
7. A history of recurring or chronic infections, any other indication of reduced immune function considered to be clinically significant by the Investigator, or any other underlying conditions which may further predispose patients to serious infection.

8. A history of lymphoma, myeloma (monoclonal hypergammaglobulinemia) or monoclonal gammopathy of unknown significance (MGUS), or any other malignancies within the past 5 years (except basal cell or squamous cell carcinoma of the skin that has been cured).
9. A diagnosis of fibromyalgia, or a diagnosis of significant depression or anxiety that in the opinion of the investigator would confound the interpretation of the study results.
10. Severe renal impairment (e.g., estimated glomerular filtration rate < 30 mL/min), moderate or severe hepatic impairment (e.g., Child-Pugh B or C) or other clinically significant hepatic disease (e.g., AST, ALT or GGT > 2x upper limit of normal).
11. Current or a history of severe, progressive or uncontrolled hematologic, gastrointestinal, endocrine, pulmonary, cardiac, or neurologic disease, or any other concomitant disease or condition or any clinically significant finding at screening that could interfere with, or for which the treatment of might interfere with, the conduct of the study, or that would, in the opinion of the Investigator, pose an unacceptable risk to the individual in this study.
12. Participation in an investigational drug or device study within 3 months prior to screening.
13. Inability to comply with the study protocol for any other reason.
14. *Women who are lactating, breastfeeding or planning to nurse.*
15. *Using other prohibited medication (moderate or potent inhibitors of CYP3A4; strong inducers of CYP3A4; strong inhibitors of the transporter P-glycoprotein [P-gp]; sensitive substrates of CYP3A4 with a narrow therapeutic index).*

4.3 METHOD OF TREATMENT ASSIGNMENT AND BLINDING

4.3.1 Treatment Assignment

Subjects will be randomly assigned to RO5459072 or placebo treatment groups in a 1:1 ratio using interactive voice/web-based response system IxRS (IvRS and IwRS).

4.3.2 Blinding

This is a double-blind study. Blinding to study treatment allocation will be achieved through use of matching-placebo capsules. Neither the patient, nor the Investigator, nor the Sponsor will be aware of the treatment allocation. The randomization list will, however, be made available to the staff at bioanalytical laboratories, to the Sponsor personnel responsible for pharmacokinetic and pharmacodynamic bioanalysis and to programmers.

4.3.3 Emergency Unblinding

In the event of an emergency, the treatment code for an individual patient will be readily available to the Investigator and Sponsor through the IxRS. If unblinding is necessary for patient management (in the case of a serious adverse event), the Investigator will be

able to break the treatment code by contacting the IxRS. Treatment codes should not be broken except in emergency situations. If the Investigator wishes to know the identity of the study drug for any other reason, he or she should contact the Medical Monitor directly. The Investigator should document and provide an explanation for any premature unblinding (e.g., accidental unblinding, unblinding due to a serious adverse event).

As per Health Authority reporting requirements, the Sponsor will break the treatment code for all unexpected serious adverse events (see Section 5.1) that are considered by the Investigator to be related to study drug.

Whenever disclosure of the identity of the study drug is necessary, adequate procedures will be in place to ensure integrity of the data. Any unblinding, at the investigating site end, will be documented in the study report with date, reason for identifying the drug and the name of all the person(s) who had to be unblinded.

4.4 STUDY TREATMENT

4.4.1 Formulation, Packaging, and Handling

4.4.1.1 RO5459072 and Placebo

The investigational medicinal products (IMPs) in this study are:

- RO5459072 50 mg capsules for oral administration (Formulation F03).
- Placebo capsules for oral administration (Formulation F04).

All IMPs will be supplied and packaged by the Sponsor.

Reddish brown, hard gelatin capsules for oral administration will be provided. The capsule fill consists of RO5459072 drug substance only. Matching-placebo capsules are also provided. The capsule fill for the matching-placebo consists only of the inactive ingredient lactose monohydrate of compendial grade.

Study drug packaging will be overseen by the Roche clinical trial supplies department and bear a label with the identification required by local law, the protocol number, drug identification and dosage. Capsules of RO5459072/Placebo should be stored according to the details on the product label (“Do not store above 25°C, protected from light, keep container tightly closed”; see Pharmacy Manual for further details).

The packaging and labeling of the study medication will be in accordance with Roche standard and local regulations.

Upon arrival of investigational products at the site, site personnel should check them for damage and verify proper identity, quantity, integrity of seals and temperature conditions, and report any deviations or product complaints to the monitor upon discovery.

For further details, see the [Investigator's Brochure](#) (Section 3.2).

